## 7 STUDY SCHEDULE

Study Event	Baseline	Perioperative (approximate minutes after delivery)			Postoperative (approximate hours after delivery)				Outpatient (approximate days after delivery)	
		20	40	100	2	6	24	48	21	42
Informed consent	✓									
Eligibility/ Demographics	✓									
Randomization	✓									
Blood Sample Collection	✓	✓	✓	✓						
Maximum intraoperative pain (NRS, 0-10) score					✓					
Adverse Effects				✓	✓	✓				
Breastfeeding Success							✓	✓		
Surgical Site Pain (NRS)					✓	✓	✓	✓	✓	✓
EPDS	✓					✓	✓	✓	✓	✓
GAD 7	✓					✓	✓	✓	✓	✓
ANRQ	✓									

**Table 6:** Study schedule

## 8 OBSERVATIONS AND MEASUREMENTS

### 8.1 Primary outcome measures

- 8.1.1 **FM1:** Establish that the incidence of PPD in our cohort is >10%
- 8.1.2 **FM2:** Achieve the recruitment of >50% of approached patients to demonstrate feasibility for an RCT
- 8.1.3 **FM3:** Ensure that the design of assessments and data collection make it possible to achieve a complete dataset in >90% of participants
- 8.1.4 **FM4:** Ascertain that neither of the chosen routes of administration of ketamine are intolerable to patients, as defined as the incidence of one or more severe side effects experienced by >10% of participants in that study arm.

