## SYNOPSIS

Study Title	Postpartum depression after Cesarean delivery: Ketamine as a preventative intervention. A feasibility pilot-study (PoCKet Pilot).												
Primary Objective	To assess the feasibility of the study by establishing: a) the incidence of PPD in our cohort; b) the acceptability to eligible patients; c) the ability of the investigative team to collect the data and; d) the tolerability of the interventions.												
Hypothesis	We hypothesize that ketamine reduces the incidence of postpartum depression (PPD) when administered at cesarean delivery and that the subcutaneous route is well tolerated and has a favorable pharmacokinetic profile.												
Study Period	Planned enrolment duration: 52 weeks Planned study duration: 58 weeks												
Number of Participants	60 patients (20 in each of the subcutaneous [SC], intravenous [IVI] and control [P] groups)												
Study Intervention	Patients in each group will receive both subcutaneous (s/c) and intravenous (i.v.) administration of their corresponding injectate shortly after delivery of their baby. The injectate will consist of either 0.9% Sodium Chloride (N/S) or 50 mg/ml ketamine (Ket) depending on their group allocation. The s/c injectate will be administered undiluted whereas the i.v. injectate will be diluted to make up a 40 ml infusion. 
  
 Groups	s/c injectate	i.v. injectate	
   
 SC:	Ket	N/S	
 
 IVI:	N/S	Ket	
 
 P:	N/S	N/S	
  
	Groups	s/c injectate	i.v. injectate	SC:	Ket	N/S	IVI:	N/S	Ket	P:	N/S	N/S
Groups	s/c injectate	i.v. injectate											
SC:	Ket	N/S											
IVI:	N/S	Ket											
P:	N/S	N/S											
Study Design	A randomised, double-blind, placebo-controlled feasibility pilot study												

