## 5 STUDY DESIGN

- 5.1 This will be a double-blinded, placebo-controlled, feasibility pilot study. The primary outcomes are related to the ability of the study procedures to gather data on the interventions' efficacy in preventing postpartum depression. Successful attainment of the following feasibility milestones (FM) is necessary to justify proceeding with a pragmatic clinical trial:
  - 5.1.1 **FM1:** Establish that the incidence of PPD in our cohort is >10%
  - 5.1.2 **FM2:** Achieve the recruitment of >50% of approached patients to demonstrate feasibility for an RCT
  - 5.1.3 **FM3:** Ensure that the design of assessments and data collection make it possible to achieve a complete dataset in >90% of participants

5.1.4 **FM4:** Ascertain that none of chosen routes of administration of ketamine is intolerable to patients, as defined as the incidence of one or more severe side effects experienced by >10% of participants in that study arm.

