## 6 STUDY PROCEDURES

6.1 Participants will be assigned to one of three intervention groups (Table 2).

Groups	Subcutaneous injectate	Intravenous injectate*
SC (n=20)	50 mg/ml ketamine	0.9% Sodium Chloride
IVI (n=20)	0.9% Sodium Chloride	50 mg/ml ketamine
P (n=20)	0.9% Sodium Chloride	0.9% Sodium Chloride

**Table 2:** Intervention groups. \*the i.v. injectate will be diluted up to a 40 ml infusion.

6.2 Participants will have baseline data (Table 3) recorded on the relevant case report form on the day of delivery. This data will include demographics to assess the performance of randomization procedures as well as characteristics that have been demonstrated to confer an increased risk of PPD. The patient will be prepared for cesarean as per institutional protocols.

Measure	Units/values
Age	Years
Height	Metres
Weight (day of surgery)	Kilograms
Gestational age	Weeks
Ethnicity	White, Black/African American, Asian, Native American/Alaskan natives, Native Hawaiian, Pacific Islander, Hispanic/Latino
Insurance status	Insured/uninsured
Psychiatric history	PPD, major depressive disorder (MDD), anxiety, premenstrual syndrome (PMS), premenstrual dysphoric disorder (PMDD), mood disorder, personality disorder, psychotic disorder
Current anxiety and depressive symptoms	EPDS and GAD-7
Psychosocial stress	ANRQ

**Table 3:** Baseline data

Once an adequate sensory block is achieved, surgery will commence. Upon delivery of the baby, 0.01 ml/kg of the “*subcutaneous injectate*” will be injected subcutaneously and the “*intravenous injectate*” will be made up to a 40ml infusion (Table 4) and commenced at 60 ml/hr. Both injectates will be administered/initiated approximately 0 - 5 minutes after delivery by the anesthetic provider via one of the cannulae that they will be using for standard patient care. The intravenous study infusion will be prepared by a member of the investigative team, who will not be involved in data collection.

---

Add 0.01 ml/kg of the “*IVI study solution*” to a 60ml syringe and use 0.9% sodium chloride to dilute the solution to 40ml.

---

**Table 4:** Instructions for preparing the “*IVI study infusion*”

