### Measurements:

1. Baseline data
2. EPDS and GAD-7 scores at baseline and approximately 1, 2, 21 and 42 days postpartum

3. ANRQ at baseline
4. Time of delivery of baby
5. Total intraoperative dose of any analgesic/sedative medication
6. Incidence of hypo- or hypertension (systolic BP < 80 or > 170 mmHg, respectively) and brady- or tachycardia (pulse < 40 or > 120 bpm, respectively)
7. Maximum intraoperative pain (numerical rating scale [NRS], 0-10)
8. Incidence of the signs/symptoms in Table 5 will be assessed intraoperatively and approximately 2 and 6 hours after delivery. The presence of each adverse effect will be assessed using a 4-point scale (absent, mild, moderate, severe).

Nausea	Shivering	Blurred vision
Vomiting	Anxiety	Diplopia
Pruritus	Euphoria	Nystagmus
Dizziness	Hallucinations	
Sedation	Amnesia	

**Table 5:** Adverse effects

9. Surgical site pain (NRS) at 2, 6, 24 and 48 hours, as well as 21 and 42 days, postpartum.
10. Opiate consumption in the first 48 hours (measured in morphine equivalents) will be calculated.
11. Plasma concentrations of ketamine at baseline and approximately 20, 40 and 100 minutes postpartum.

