### 8.2 Secondary outcome measures

- 8.2.1 Intraoperative supplementary analgesia
- 8.2.2 Intraoperative hypo/hypertension and brady-/tachycardia
- 8.2.3 Maximum intraoperative pain (NRS)
- 8.2.4 Adverse effects intraoperatively and at approximately 2 and 6 hours postpartum
- 8.2.5 Plasma concentrations of ketamine at baseline and approximately 20, 40 and 100 minutes postpartum. Samples will be centrifuged and the extracted plasma samples will be stored at -80 degrees Celsius before transfer to the metabolomics laboratory at Washington University for ketamine assay.
- 8.2.6 Total opiate consumption in the first 2 days postpartum
- 8.2.7 Surgical site pain (NRS 0-10), by face-to-face or telephone interview, at 2, 6, 24 and 48 hours after delivery and on postpartum days 21 and 42.
- 8.2.8 EPDS and GAD-7 on postpartum days 1 and 2, by face to face interview, and days 21 and 42, by telephone interview.
- 8.2.9 Apgar scores
- 8.2.10 Admission to NICU
- 8.2.11 Breastfeeding success (Y/N) on post-operative days 1 and 2

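### Can the data-completeness milestone (FM3) be met by leaving lost women out of its denominator?

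*Combined protocol and SAP*

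**What the plan says.** FM3 appears in the same words in Sections 5.1.3 and 8.1.3: the assessments and data collection should "make it possible to achieve a complete dataset in >90% of participants". Section 5.1 says that attaining the milestones "is necessary to justify proceeding with a pragmatic clinical trial". The matching aim in the Synopsis is "the ability of the investigative team to collect the data".

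On who is counted, the Synopsis plans "60 patients (20 in each of the subcutaneous" and the other two groups, and Section 6.1 states: "Participants will be assigned to one of three intervention groups". Table 6 puts randomisation at baseline. Treatment comes later: "Both injectates will be administered/initiated approximately 0 - 5 minutes after delivery".

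On what is collected, item 2 of the Section 6 measurement list has "EPDS and GAD-7 scores at baseline and approximately 1, 2, 21 and 42 days postpartum". Section 8.2.8 gives the same postpartum days, with days 1 and 2 face to face "and days 21 and 42, by telephone interview". Table 6 also ticks EPDS and GAD-7 at 6 hours. Section 9 covers descriptive summaries and pharmacokinetics. It gives no analysis population, no rule for missing entries and no method for FM3.

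**The concern.** FM3 is a primary outcome and a condition for the next trial, yet its whole definition is one clause. Three things are not written down: whether a woman who withdraws, is randomised but not treated, or is not reached by telephone stays in the denominator; how a partly filled record scores; and which items make a dataset complete.

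The women lost to follow-up are the failures that a data-collection milestone exists to count. If they could be removed once the data are in, FM3 could be met because they were lost. The threshold is strict and the trial small, so moving one or two women can reverse the result. The 6-hour EPDS/GAD-7 tick in Table 6 adds doubt about which entries are required.

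**Working it through.** **Inputs from the protocol.** Threshold: complete/n strictly above 0.90 (5.1.3, 8.1.3). Planned n: 3 × 20 = 60 (Synopsis, Table 2). The protocol states no expected completion rate and no FM3 count, so there is no published figure to reproduce beyond the 60. Every completion rate below is an assumption.

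**1. The plain reading.** With n = 60, 0.90 × 60 = 54. The inequality is strict, so 55 are needed: 55/60 = 91.7% passes and 54/60 = 90.0% fails. At most five women may be incomplete.

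**2. How much selective removal could do.**

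| Complete | Of all 60 | Incomplete women removed | Result |
|---|---|---|---|
| 54 | 90.0% | 1 | 54/59 = 91.5% |
| 53 | 88.3% | 2 | 53/58 = 91.4% |
| 52 | 86.7% | 3 | 52/57 = 91.2% |
| 49 | 81.7% | 6 | 49/54 = 90.7% |

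Every row fails on 60 and passes after removal. Each pass requires taking out some incomplete women and keeping five others. Removing all six from the first row gives 54/54 = 100%. Applied to every incomplete record, the same rule gives 100% whatever happens, so it cannot be what a completeness milestone means.

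**3. The same contrast as a probability.** Assume that in-hospital items are always complete and that the two calls are independent, each completed with probability c. With all 60, p = c² and the chance of meeting FM3 is P(X ≥ 55), X ~ Bin(60, p). If only women reached at day 42 count, n ~ Bin(60, c), X given n ~ Bin(n, c), and P(X > 0.9n) is summed over n.

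| c | All 60 | Reached at day 42 only |
|---|---|---|
| 0.97 | 0.858 | 0.992 |
| 0.95 | 0.463 | 0.935 |
| 0.93 | 0.162 | 0.804 |

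The gaps are large, but they set the plain reading against one that the text does not support. They show what misuse would do, not what the plan is likely to produce.

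**4. The item set.** Table 6 has 29 ticked measurement cells: blood samples 4, maximum intraoperative pain 1, adverse effects 3, breastfeeding 2, surgical-site pain 6, EPDS 6, GAD-7 6, ANRQ 1. Suppose every cell must be filled and each is filled independently with probability 0.99. Then p = 0.99^29 = 0.747 and P(X ≥ 55) is about 0.001. Suppose instead that only the three post-delivery blood samples and the two calls are required, each at 0.98. Then p = 0.98^5 = 0.904 and P(X ≥ 55) is about 0.48. With the two calls alone at 0.98, p = 0.98² = 0.960 and the probability is 0.97. The choice of items and the scoring of partial records therefore move the result at least as much as the denominator does.

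**5. The lists side by side.** Table 6 has the 6-hour EPDS/GAD-7; Section 6 item 2 and 8.2.8 do not. Apgar scores, NICU admission and breastfeeding are in 8.2 but not in the Section 6 measurement list. Opiate consumption and haemodynamic events are in Section 6 but have no row in Table 6. None of these lists is named as the content of FM3.

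**The case for a change.** The strongest case for a change is that a go/no-go criterion should leave no choice open once the data are seen, and that fixing this one costs only a few lines. FM4, in the same list, names both its event and its set of women (the study arm). FM3 names neither its items nor the treatment of women randomised but not given the injectate. The result can turn on one woman, and the lists differ in more than the 6-hour entry.

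Much of this stands as description: the arithmetic is right, and no passage ties an item list or a missing-entry rule to FM3. It does not follow that the denominator is missing. A woman who cannot be reached by telephone is still a participant, and the planned number is given. Writing down that all randomised women count would record what an analyst would do anyway.

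On the items, the obvious remedy is that any missing entry makes a woman incomplete. That is one scoring rule among several; key items only, or a permitted fraction, are others. If Table 6 were the list, its cost would be the chance of about 0.001 shown above. Which items matter is for the sponsor to decide, and nothing in the documents points to a single answer. Reconciling the 6-hour tick alone would not settle what complete means, and would alter no stated conclusion.

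**Conclusion.** No change to the plan follows. Read as written, FM3 has all 60 randomised women in its denominator and needs at least 55 complete. Six women missed at day 42 give 54/60 = 90.0% and a fail, provided day-42 items count. That is the result a data-collection milestone should give. The passing alternatives, from 54/59 to 54/54, depend on removing women because their data are missing, which the protocol nowhere suggests.

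What remains is a gap in detail: the items and time points of a complete dataset, the scoring of partial records, and differences between Table 6, Section 6 and Section 8.2. A report that gives the number complete out of 60 and names the items counted would deal with it. The conclusion rests on reading participants as all women randomised and on analysts keeping to that reading. The probabilities rest on assumed completion rates and independence and serve only as illustration.

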### 8.2 Secondary outcome measures

- 8.2.1 Intraoperative supplementary analgesia
- 8.2.2 Intraoperative hypo/hypertension and brady-/tachycardia
- 8.2.3 Maximum intraoperative pain (NRS)
- 8.2.4 Adverse effects intraoperatively and at approximately 2 and 6 hours postpartum
- 8.2.5 Plasma concentrations of ketamine at baseline and approximately 20, 40 and 100 minutes postpartum. Samples will be centrifuged and the extracted plasma samples will be stored at -80 degrees Celsius before transfer to the metabolomics laboratory at Washington University for ketamine assay.
- 8.2.6 Total opiate consumption in the first 2 days postpartum
- 8.2.7 Surgical site pain (NRS 0-10), by face-to-face or telephone interview, at 2, 6, 24 and 48 hours after delivery and on postpartum days 21 and 42.
- 8.2.8 EPDS and GAD-7 on postpartum days 1 and 2, by face to face interview, and days 21 and 42, by telephone interview.
- 8.2.9 Apgar scores
- 8.2.10 Admission to NICU
- 8.2.11 Breastfeeding success (Y/N) on post-operative days 1 and 2

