## 9 STATISTICAL METHODS

### 9.1 Sample size and analysis

No formal sample size has been performed as this is a pilot designed to establish the feasibility of an RCT. Preliminary data from this study will be used to inform the sample size calculation for the subsequent clinical trial. Descriptive statistics will be employed to present the demographic data. Continuous variables will be summarized using means (SD) or medians (IQR), as appropriate. After construction of the concentration-time curves for each patient, the peak plasma concentration and area under the concentration-time curve will be summarized overall and associations with both antidepressant effect and incidence of adverse symptoms will be explored.

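### FM4 and the intraoperative outcomes are not restricted to the time after dosing, so severe Table 5 effects that precede any study drug can count against a ketamine route

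*Combined protocol and SAP*

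**What the plan says.** Section 6.2 sets the order of events: "Once an adequate sensory block is achieved, surgery will commence", and then, after the baby is born, "Both injectates will be administered/initiated approximately 0 - 5 minutes after delivery". Every operation therefore has a stretch with no study drug on board, in all three arms.

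The outcomes are defined by the operation, not by dosing:

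- Haemodynamics (8.2.2): "Intraoperative hypo/hypertension and brady-/tachycardia". The Measurements list adds blood pressure and pulse cut-offs but no time window.
- Adverse effects (Measurements item 8, Table 5): these "will be assessed intraoperatively and approximately 2 and 6 hours after delivery". No start point is given for the intraoperative part.
- Pain (8.2.3) is a maximum over the operation, and supplementary analgesia (8.2.1; Measurements item 5) is a total over the operation.

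Severity is graded only for the Table 5 signs and symptoms: "The presence of each adverse effect will be assessed using a 4-point scale (absent, mild, moderate, severe").

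FM4 (5.1.4 and 8.1.4) calls a route intolerable "as defined as the incidence of one or more severe side effects experienced by >10% of participants in that study arm". Section 5.1 makes meeting the milestones a condition for going on to a pragmatic trial. The Synopsis plans "60 patients (20 in each of the subcutaneous [SC], intravenous [IVI] and control [P] groups").

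Table 6 places the first adverse-effect tick in the 100-minute column, timed from delivery, and has none at baseline. Measurements item 4 records the time of delivery; no item records when the injectates start.

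**The concern.** FM4 is meant to say whether a route of giving ketamine is tolerable. Table 5 includes nausea, vomiting, pruritus, shivering and anxiety, which neuraxial anaesthesia or surgery could also plausibly produce. If one of these is severe between incision and delivery, ketamine cannot have caused it. Yet nothing in FM4 or item 8 keeps it out of the count, and without a pre-dose assessment it may not be identifiable afterwards.

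Because FM4 is a fixed limit applied to each ketamine arm alone, randomisation and blinding do not protect it. An equal background in all three arms still pushes a ketamine arm towards failure. What is at stake is a stop/go decision on 20 women per arm, in which a tolerable route could be judged intolerable.

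**Working it through.** **Inputs from the documents.** There are 20 women per arm (Synopsis, Table 2), two ketamine arms, and an FM4 limit of more than 10%. Section 9.1 states "No formal sample size has been performed as this is a pilot designed to establish the feasibility of an RCT", so there is no power or error rate to reproduce. The stated total agrees: 3 × 20 = 60.

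**Decision rule.** 2/20 = 10% is not above the limit and 3/20 = 15% is. An arm fails at 3 or more of 20, if all 20 are assessed.

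**Assumed inputs, because the documents give none.** Let d be the proportion with a severe Table 5 effect after dosing and b the proportion with one before dosing. The proportion p counted by FM4 depends on how far these are the same women:

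- independent within a woman: p = 1 − (1 − d)(1 − b);
- full overlap: p = max(d, b).

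**Formulas.** One arm passes with probability q(p) = Σ C(20,k) p^k (1 − p)^(20−k), summed over k = 0, 1, 2. With independent arms, both pass with probability q(p)².

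Example at p = 0.05: q = 0.3585 + 0.3774 + 0.1887 = 0.9245, and 0.9245² = 0.855.

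**Chance that both routes pass, d = 5%**

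| Pre-dose rate b | p, independent | Both pass | p, full overlap | Both pass |
|---|---|---|---|---|
| 0% | 0.0500 | 85% | 0.05 | 85% |
| 2% | 0.0690 | 71% | 0.05 | 85% |
| 5% | 0.0975 | 48% | 0.05 | 85% |
| 10% | 0.1450 | 18% | 0.10 | 46% |

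With d = 2% and independence, the figures for b = 0%, 2%, 5% and 10% are 98.6%, 91.6%, 71.2% and 33.0%.

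**Background events in general.** Suppose ketamine caused no severe effect at all. A background rate of 2%, 5%, 10% or 15%, before or after dosing, would fail a given arm with probability 0.7%, 7.6%, 32.3% or 59.5%, and at least one of the two arms with probability 1.4%, 14.5%, 54.2% or 83.6%. A post-dose window removes only the part of this that arises before dosing.

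**Outcomes outside FM4.** For a yes/no outcome such as hypotension, with pre-dose and post-dose events independent, the arm difference shrinks by the factor (1 − b). As an illustration only, 10% against 20% after dosing with b = 30% becomes 1 − 0.7 × 0.9 = 37% against 1 − 0.7 × 0.8 = 44%, so 10 points become 7. The direction of the comparison is unchanged.

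**The case against.** **Table 6 times the first adverse-effect assessment from delivery.** If the period covered also runs from delivery, the undosed part is at most a few minutes. But the tick shows when an assessment is made, not what it covers: the same table ticks maximum intraoperative pain at 2 hours, which plainly looks back. A reader might infer that all four outcomes are expressly counted over the whole operation. The documents do not say that for adverse effects or haemodynamics, where the window is simply unrestricted. It is the ordinary meaning only for maximum pain and total dose.

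**Hypotension, tachycardia or pain might be thought to trip FM4.** The text does not support this. Only Table 5 effects carry a severe grade; blood pressure, pulse, pain scores and supplementary drugs are not in Table 5 and are not named in FM4. They are secondary outcomes in a randomised, double-blind pilot with no planned between-arm test, so pre-dose time dilutes or adds noise and does not bias the comparison.

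**Section 10.3 already asks for onset time and relationship to study drug.** It does, in general adverse-event reporting, and the term side effects can be read as drug-related. But that term is not defined, and neither onset nor relationship is linked to FM4. This makes the repair easier; it does not make it unnecessary.

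**The rates are assumed, and independence is the unfavourable case.** This stands. Under full overlap the loss is nil at pre-dose rates of 2% and 5%, so the table is a range and not an estimate.

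**Conclusion.** The point holds for FM4 and the Table 5 effects. As written, a severe effect that arises before any study drug can count towards the 3 of 20 that fails a route, and no onset, attribution or placebo condition prevents it. For 8.2.1–8.2.3 the consequence is limited to dilution or noise.

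The size is unknown, because no event rate is given. With an assumed 5% post-dose severe rate, both routes pass with probability 85% when there are no pre-dose events. At a 5% pre-dose rate the range is 48% to 85%, and at 10% it is 18% to 46%, according to how far the same women are affected. These figures assume independent arms and 20 assessed women in each. The change should be made, because FM4 is a stop/go criterion, the repair is small, and the missing pre-dose information may not be recoverable later.

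**What to change.** - **FM4 (5.1.4, 8.1.4) and 8.2.4:** state that FM4 counts the Table 5 effects graded severe, and only those with onset or worsening after the start of injectate administration (the first of the two injectates). Report earlier events separately as baseline.
- **Case report form:** record the injectate start time beside the delivery time, add a Table 5 check before dosing, and use the onset time that section 10.3 already requires.
- **8.2.1–8.2.3:** report the period after injectate start separately from the period before it.
- **Reporting of FM4:** show the placebo arm's severe-effect rate beside those of the two ketamine arms, because a post-dose window does not remove anaesthetic or surgical effects that arise after dosing, including at 2 and 6 hours.

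The cost is a wording change and a few form fields: start time, pre-dose check, and a before/after split for the pain score and supplementary drugs. No visits are added.

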Eligibility Criteria	
Inclusion criteria
 
 
1. Term pregnancy
 
2. Age 18-45 years of age
 
3. Scheduled cesarean delivery under neuraxial anesthesia
 
 
Exclusion criteria
 
 
1. ASA classification IV or V
 
2. History of psychotic episodes
 
3. History of allergy to ketamine
 
4. Inability to communicate in English or any other barrier to providing informed consent
 
												
Measurements	
 
Psychosocial stress (Antenatal Risk Questionnaire [ANRQ])
 
Weight (kg) and height (m)
 
Time of delivery of baby
 
Total intraoperative dose of analgesic/sedative medication
 
Baseline and intraoperative vital signs
 
Maximum intraoperative pain (NRS)
 
48-hour total opiate consumption (morphine equivalents)
 
Apgar scores at 1 and 5 minutes postpartum
 
Admission to NICU
 
												

	
 
j) Pain originating from surgical site (NRS 0-10): 2, 6, 24 and 48 hours and 21 and 42 days postpartum.
 
k) Edinburgh Postpartum Depression Scale (EPDS) and Generalized Anxiety Disorder 7-item (GAD-7) Scale: Day of surgery and postpartum days 1, 2, 21 and 42
 
l) Plasma concentrations of ketamine at baseline, 20, 40 and 100 minutes after administration
 
m) Breastfeeding success (Y/N): postpartum days 1 and 2
 
n) Adverse effects, intraoperatively and at 2 and 6 hours postpartum (absent, mild, moderate or severe)
 

Statistical Methodology	
Descriptive statistics will be employed to present the demographic data. Continuous variables will be summarized using means (SD) or medians (IQR), as appropriate. After construction of the concentration-time curves for each patient, the peak plasma concentration and area under the concentration-time curve will be summarized overall and associations with both antidepressant effect and incidence of adverse symptoms will be explored.
 
NONMEM® 7.4 (ICON Development Solutions) software will be utilised to assess pharmacokinetic profile of ketamine by each route.

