### 1.3 Ketamine and PPD

This promising anti-depressant effect has prompted investigation of ketamine as a preventative measure in patients undergoing CD. There have been 2 studies to date, one which failed to demonstrate any benefit from a bolus dose of 0.25 mg/kg and one which documented a large reduction (1 and 22% in the treatment and control, respectively) in the (6 week) period prevalence of postpartum depression after a 4 mg/kg dose of ketamine over 50 hours (~0.08 mg/kg/hr).

The prolonged IV infusion, in the Jianxin (2015) study, was achieved by adding the ketamine to a sufentanil patient-controlled analgesic (PCA) pump with a background infusion. This PCA pump is a standard part of their post-cesarean analgesic regimen. In our institution, it is standard practice to discontinue IV infusions and to remove IV cannulae as early as it is safe to do so. This practice is essential to the attempts to enhance postoperative recovery and aid mother's bonding with their babies and facilitate their early-

life care. This reflects patients' expectations and preferences and is in line with other maternity units across North America and Europe.

The natural course of PPD varies and, although it may resolve spontaneously within weeks, approximately 20% of women with PPD still have depression at 12 months and beyond. As many as 13% will still have depressive symptoms at 2 years and 40% will have a relapse. Considering the maternal suffering, disruption to the family, potential impairment of the social, emotional, and cognitive development of the child, and the rare cases of infanticide and suicide caused by PPD, the impact on families and society as a whole is difficult to overemphasize. An intervention that promises such a large reduction in this devastating disease warrants extensive research. In an attempt to achieve the benefit demonstrated by Jianxin et al. whilst employing methods more acceptable to our patients we have designed a pilot study to assess the feasibility of our study design and collect preliminary tolerability and efficacy data on ketamine administered by two alternative routes: 40-minute IV infusion (i.v.) and subcutaneous (s.c.) injection.

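### The blood pressure and pulse outcome is tied to the operation, not to time since dosing, so it can close before the 40-minute infusion ends and may not be comparable between routes

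*Combined protocol and SAP*

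**What the plan says.** Four places in the combined protocol and SAP bear on when blood pressure and pulse are collected.

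- Section 8.2.2 gives the outcome as "Intraoperative hypo/hypertension and brady-/tachycardia".
- The Synopsis, under Measurements, lists "Baseline and intraoperative vital signs".
- Section 6, Measurements, item 6 gives thresholds but no time window or reading frequency: "Incidence of hypo- or hypertension (systolic BP < 80 or > 170 mmHg, respectively) and brady- or tachycardia (pulse < 40 or > 120" bpm.
- Section 7, Table 6 has no vital-signs row at any time point.

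Table 5, the list of adverse effects graded intraoperatively and at about 2 and 6 hours, does not include blood pressure or pulse.

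On dosing, section 6 says that the intravenous injectate is "made up to a 40ml infusion (Table 4) and commenced at 60 ml/hr", and that "Both injectates will be administered/initiated approximately 0 - 5 minutes after delivery". Section 1.3 describes the two routes as "40-minute IV infusion (i.v.) and subcutaneous (s.c.) injection". Blood sampling runs later than the infusion; section 8.2.5 has "Plasma concentrations of ketamine at baseline and approximately 20, 40 and 100 minutes postpartum".

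**The concern.** The pilot is meant to give preliminary tolerability data on two routes of ketamine and to inform a later trial. A drug-effect outcome is easiest to interpret when everyone is observed over the same period after dosing. Here the period is set by the surgery, with three consequences.

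1. Surgery starts before delivery and the study drug is given after it. An event between the start of surgery and dosing meets the outcome definition although no study drug has been given.
2. Time at risk after dosing differs from woman to woman with surgical duration, so incidence per woman is not on a common basis.
3. If surgery ends before the infusion does, the last part of the infusion is unobserved. With constant-rate input and first-order elimination the plasma level rises until the infusion stops, so the part lost is the part with the highest exposure. If the haemodynamic effect rises with concentration, IVI would look closer to placebo than it is.

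Symptoms are followed to 6 hours and plasma to 100 minutes. The haemodynamic outcome is worded to stop with surgery, and no reason is given. Readings that were not recorded may be impossible to recover later.

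**Working it through.** **Inputs from the documents.** Infusion volume 40 ml, rate 60 ml/hr, start 0 to 5 minutes after delivery (section 6); stated duration 40 minutes (section 1.3); last blood sample at about 100 minutes (section 8.2.5); 20 women per arm, 60 in all (Synopsis).

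**Not in the documents.** The time from delivery to end of surgery, a definition of intraoperative, and the time to peak by the subcutaneous route.

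**Step 1: the plan's own figure.** Duration = 40 ml ÷ 60 ml/hr × 60 = 40 minutes, which agrees with section 1.3. The infusion ends at 0 + 40 = 40 to 5 + 40 = 45 minutes after delivery.

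**Step 2: share of the infusion inside the window.** Share = (end of surgery − start) ÷ 40, capped at 1. End of surgery is assumed, in minutes after delivery.

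| End of surgery (assumed) | Start at 0 min | Start at 5 min |
|---|---|---|
| 20 min | 20/40 = 50% | 15/40 = 37.5% |
| 30 min | 30/40 = 75% | 25/40 = 62.5% |
| 40 min | 40/40 = 100% | 35/40 = 87.5% |
| 45 min or later | 100% | 100% |

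The infusion is cut off only if surgery ends less than 40 to 45 minutes after delivery.

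**Step 3: does early closure favour one route?** This uses a one-compartment illustration with both routes started at delivery and every kinetic value assumed: elimination half-life 20, 60 or 150 minutes and subcutaneous absorption half-life 5, 10, 20 or 40 minutes. With ke and ka equal to ln 2 divided by the respective half-life:

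- IV level during infusion is proportional to 1 − exp(−ke·t), so the peak is always at 40 minutes.
- SC level is proportional to exp(−ke·t) − exp(−ka·t), scaled by ka/(ka − ke). Its peak falls anywhere from 13 to 104 minutes across the twelve combinations.

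Highest level reached inside the window, as a share of the true peak:

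| End of surgery (assumed) | IV | SC |
|---|---|---|
| 30 min, all combinations | 0.77 to 0.86 | 0.61 to 1.00 |
| 30 min, half-lives 60 (elimination) and 5 (absorption) | 0.79 | 1.00 |
| 30 min, half-lives 150 and 40 | 0.77 | 0.61 |
| 50 min, all combinations | 1.00 | 0.82 to 1.00 |

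For example, IV at 30 minutes with half-life 60 is (1 − 2^(−30/60)) ÷ (1 − 2^(−40/60)) = 0.293 ÷ 0.370 = 0.79. With surgery ending at 30 minutes, IV is cut off more in ten of the twelve combinations and SC in two. The grid is a choice and carries no probabilities. With surgery ending at 50 minutes, only SC can be cut off. The sign of any difference is not fixed by the documents.

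**Step 4: a window to the 100-minute sample.** It would cover the whole infusion and leave 100 − 45 = 55 to 100 − 40 = 60 minutes after it ends.

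**The case against.** A reader might infer that IV events are under-counted relative to the subcutaneous route, because the whole subcutaneous dose is injected at the start. The documents do not support this. Drug under the skin is not yet drug in plasma, the subcutaneous time to peak is not given, and objective 2.2 is to measure both profiles. Step 3 shows that the sign can go either way.

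The remaining objections are these.

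- **Truncation is conditional.** If surgery always runs past 45 minutes after delivery, the infusion is fully covered. This stands. The documents do not say that it does, and the variable window and the time before dosing remain in any case.
- **Intraoperative-only collection is not stated everywhere.** Item 6 in section 6 has no window, and Table 6 has no vital-signs row even during surgery, so its silence about later times proves little. Table 6 also ticks adverse effects at 100 minutes, which may be where the intraoperative assessment is recorded. This stands as a reason to reconcile the sections. It does not supply a later window, since the only two places that state a period both say intraoperative.
- **Later events can be reported as adverse events.** Sections 10.1 and 10.3 allow that, but unscheduled reporting does not replace readings checked against fixed thresholds.
- **All arms follow the same rule, every woman receives both an injection and an infusion, and no test is specified.** Nothing links surgical duration to arm, so one cannot say that the comparison is biased as a matter of fact. But the same clock time can cover a different share of exposure by each route, which affects a description as much as a test.
- **The impact is small.** This stands. It is one of eleven secondary outcomes with 20 women per arm. Table 5, the only severity-graded list, omits blood pressure and pulse.

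**Conclusion.** The point holds in a limited form. The haemodynamic window follows the operation instead of the dose, includes time before any study drug, varies in length between women, and can close before the infusion ends at 40 to 45 minutes after delivery. How often it would do so cannot be known from the documents.

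If it does close early, the highest-exposure part of the infusion is missed and the IVI-versus-placebo description could be weakened. That assumes a level that rises throughout the infusion and an effect that rises with the level; it does not depend on subcutaneous absorption. For IVI versus SC, all that can be said is that the counts may not be comparable, direction unknown.

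The weight is modest. The outcome is secondary and descriptive, and no sample size or error rate depends on it. FM4 probably does not change if its severe side effects are the Table 5 items, which the documents do not state outright. The change is worth making because it is cheap and tolerability by route is part of what the pilot is for.

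**What to change.** Reconcile the Synopsis item, section 6 item 6, Table 6 and section 8.2.2 so that they describe the same outcome:

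- Define one window for all three arms, from the start of study drug to the 100-minute sample, whether or not surgery has ended. State the zero point: the Synopsis counts sampling times from administration and section 8.2.5 from delivery, which can differ by up to 5 minutes.
- State one reading frequency for all arms, the same in theatre and afterwards, so that pooling the two settings does not itself create a difference in ascertainment.
- Add a vital-signs row to Table 6.
- Summarise events per woman over that window, and report pre-drug readings separately as baseline.

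This changes what is recorded and leaves treatment as it is. The cost is a wording change, a case report form row, and recording or transcribing post-surgical readings to 100 minutes in 60 women. It assumes that routine recovery readings are available, which the documents do not describe. The 100-minute sample puts a study contact at the end of the window but does not show that staff are present throughout, so this needs checking locally.
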